To estimate FAMS' main effects and subgroup effects, we will use generalized estimating equations (GEE) with a working-independence correlation structure and identity link. Models will be adjusted for insulin use at baseline and baseline value of the outcome of interest (via a restricted cubic spline with three knots) for each model. We will allow a two-way interaction between time and condition and a two-way spline interaction between time and baseline value of the outcome. Differences between arms will be tested based on a linear combination of regression coefficients at each time point (based on Wald-based test with one degree of freedom). Point estimates and corresponding 95% confidence intervals will be obtained for each follow-up time point, to graphically display trajectories in adjusted mean outcomes difference over 15 months. We will explore subgroups effects (i.e., divided sample) to determine for whom the intervention was most or least effective using the same models as described above.

For each intervention target (**Figure 1**), we fit models as described above. Continuous measures were analyzed using the GEE model. The summative one-item physical activity measure was ordinal, and therefore analyzed using an ordinal regression model (odds ratios obtained on cumulative logit/proportional odds scale). Each model was run three times, to

estimate during (6-months), post (9-months) and sustained (15-months) intervention effects.

For mediation analyses, we model between-subjects mediation with path analysis with an SEM framework as suggested in **Figure 1**, including multiple mediators. Mediation models include intervention targets at both 6 and 9 months as mediators and a single outcome (i.e., HbA1c, diabetes distress or well-being). We ran this model separately for each outcome at 9, 12 (H1cA1c only) and 15 months. For parsimony, we restricted the number of mediators guided by findings evaluating intervention effects on these mediators, opting for continuous and sensitive mediator measure(s) of self-care behaviors unless both measures were significantly improved by the intervention. We used Amos version 29 regression imputation function to address missing data, running each imputation separately for each model.

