Path coefficients and indirect effects evaluate mediation using 2,000 bootstrap samples for bias-corrected estimates and 95% confidence intervals for effects. Paths from condition to mediators will determine if FAMS 2.0 improved each mediator relative to control, and indirect effects will identify mechanisms by which FAMS 2.0 affected outcomes. In addition to examining mediators of patient participants' outcomes, we examine dyadic mediation by assessing whether support person outcome changes are explained by change in their own involvement and/or by improvements in the patient participants' outcomes (e.g., mediator: change in patient participant HbA1c, outcome: change in support person well-being).

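### The patient mediation models specify no baseline mediator, baseline outcome or insulin term, so stable differences between patients can appear as a FAMS mechanism

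*SAP*

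**What the plan says.** For the main-effects GEE models the SAP is explicit: "Models will be adjusted for insulin use at baseline and baseline value of the outcome of interest", with the baseline outcome entered as a spline. It carries this over to each intervention target analysed as an outcome ("we fit models as described above").

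The mediation paragraph makes no such link. It says "we model between-subjects mediation with path analysis with an SEM framework", with paths taken from Figure 1. It then gives the content of the models: "Mediation models include intervention targets at both 6 and 9 months as mediators and a single outcome". Timing follows: "We ran this model separately for each outcome at 9, 12" (HbA1c only at 12) and 15 months. On the choice of mediators it says "we restricted the number of mediators guided by findings evaluating intervention effects on these mediators". Inference is by bootstrap, "using 2,000 bootstrap samples for bias-corrected estimates and 95% confidence intervals", and the reading is causal: "indirect effects will identify mechanisms by which FAMS 2.0 affected outcomes".

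The dyadic models at the end of the SAP are described differently, in terms of change in the mediator and change in the outcome.

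**The concern.** An indirect effect is the product of two paths. Randomization protects the first, from condition to mediator. It does not protect the second, from mediator to outcome, because nobody was randomized to a level of self-efficacy or family involvement. A patient who starts with high self-efficacy and low A1c will tend to have both at 6, 9 and 15 months, whatever FAMS does. In a model without baseline values, that persistence loads onto the second path.

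A false indirect effect then needs only that FAMS shifts the mediator. The SAP makes this likely, because mediators are retained partly on their observed intervention effect. The mediation part of Aim 4 (protocol section 2.0) could then credit a target that has no influence on the outcome.

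**Working it through.** **1. The plan's own figures (protocol section 8.0).** Inputs: difference 0.5%, SD 1.5%, 5% level (taken as two-sided), 80% power.
- Per arm: 2 × (1.96 + 0.842)² × (1.5/0.5)² = 141.3, so 142, or 284 in total, as stated.
- 284/0.85 = 334.1, against 334 stated.
- Detectable standardized effect on mediators: 2.80 × √(2/n per arm). At 90% retention (150.3 per arm) this is 0.323, and at 80% (133.6 per arm) 0.343, matching the stated 0.32-0.34.

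A mediator shift of 0.33-0.34 SD is therefore the plan's own scale. The documents give no figure for the mediation models.

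**2. Bias without baselines, one mediator.** Assumed, not in the documents: a share ρ of the variance of mediator and outcome is a stable trait, the two traits correlate at rs, and the mediator has no effect on the outcome. Within arm, both have variance 1 and covariance ρ × rs, so the fitted second path is b = ρ × rs.
- With ρ = 0.6 and rs = 0.4: b = 0.24. With a = 0.34 the false indirect effect is 0.34 × 0.24 = 0.082 SD.
- Simulation (N = 284, 1,000 runs) gave 0.239 and 0.081.

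**3. Bias with baseline mediator and outcome as covariates.** Take the scaled sum and difference of mediator and outcome. Their variances are 1.24 and 0.76, and their covariances with their own baselines are 0.84 and 0.36.
- Residual variances: 1.24 − 0.84²/1.24 = 0.671, and 0.76 − 0.36²/0.76 = 0.589.
- Residual covariance: (0.671 − 0.589)/2 = 0.041. Residual variance: (0.671 + 0.589)/2 = 0.630.
- b = 0.041/0.630 = 0.065, and the indirect effect is 0.34 × 0.065 = 0.022. Simulation gave 0.061 and 0.021.

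The remainder exists because one baseline reading measures the trait with error.

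**4. How often false mediation is declared, one mediator.** a = 0.34, ρ = 0.6, 95% Monte Carlo interval for a × b standing in for the bootstrap:

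| rs | no baselines | with baselines |
|---|---|---|
| 0 | 3% | 6% |
| 0.2 | 39% | 7% |
| 0.4 | 81% | 17% |
| 0.6 | 82% | 41% |

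The first column levels off near 82% because the first path must also be detected: 0.34/√(2/142) = 2.86, which gives power of about 82%. At rs = 0.4, changing ρ to 0.4 or 0.8 gives 61% or 82% without baselines and 19% or 11% with them. If FAMS does not move the mediator (a = 0), the rate without baselines is at most 5.6%.

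**5. The planned form, with 6- and 9-month mediators together.** N = 284, shift 0.33 SD, no true mediation, correlations -0.1 to -0.4, test of the total indirect effect:

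| data structure | no baselines | with baselines |
|---|---|---|
| autoregressive | 6-53% | 2-4% |
| stable latent trait | 12-81% | 4-19% |

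Steps 2-4 use positive correlations and step 5 negative ones; only the size matters for these rates.

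**The case against.** Several objections have force.

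- **Silence is not exclusion.** A reader might infer that the SAP leaves baselines out on purpose. The text does not say so. It does not call its list of model contents complete, and Figure 1 is not available to check. Protocol section 8.0 also mentions adjusting for baseline outcomes and other covariates where an analysis needs it. This stands against any claim of deliberate omission. That remark, however, sits in the power argument, names no baseline mediator and does not fix a model.
- **One mediator is not the planned model.** With both waves of one mediator entered and paths tested separately (autoregressive data), a single-mediator rate of 28% at correlation -0.2 became 18% for the 6-month path and 4% for the 9-month path. At -0.4, 74% became 59% and 4%. The per-path rates are lower, but the total indirect effect in step 5 remains inflated.
- **Balanced allocation.** Protocol section 4.0 balances the arms on baseline outcomes. That helps comparisons between arms, not the mediator-outcome path within them.
- **The dyadic models.** A reader might extend the point to these. They are written as change, so baseline already enters. In the simulation of step 4, change scores gave 4-5% false mediation, although only because that simulation assumes an additive stable trait. The documents give no ground for altering them.
- **Baseline adjustment as a complete cure.** It is not one: step 4 leaves 7-41% for rs of 0.2 to 0.6.

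**Conclusion.** The point holds for the patient mediation models as written. No baseline term is specified, and without one the mediator-outcome path can reflect stable differences between patients. Under the assumptions above, a false total indirect effect appears in roughly 6-81% of trials without baselines and roughly 2-19% with them. The width of these ranges comes from the correlation, the stability and the data structure, all of which are assumed.

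Two stronger readings are not supported. The first is that false mechanisms will be reported. That requires both that FAMS moves the mediator and that the traits are correlated; if either fails, the simulated rate stays near or below the nominal 5%. The second is that the trial's main result is in doubt. The GEE comparisons of A1c, the secondary outcomes and the intervention targets are specified with baseline adjustment and do not depend on these models. The point is confined to the mediation part of Aim 4. It is worth correcting before mediation results are interpreted, but it does not threaten the trial's primary conclusion.

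**What to change.** In the SAP's mediation paragraph:

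1. State that each patient mediation model regresses every mediator and the outcome on condition, the baseline values of all mediators in that model, the baseline outcome, and insulin use at baseline. If the models already do this, one sentence saying so settles this item.
2. Add a sensitivity analysis for remaining mediator-outcome confounding, for example the residual correlation between mediator and outcome at which each indirect effect would vanish.
3. Describe indirect effects as conditional on no unmeasured mediator-outcome confounding, instead of as identifying mechanisms outright.

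Leave the dyadic change-score models as they are.

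The cost is SAP wording and a rerun of the path models. Surveys and A1c were collected at baseline (protocol section 5.0), and baseline insulin use is already required by the GEE models, so no new data are needed. Some indirect effects may become smaller.

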5.0 Study Procedures

Procedure/Activity	Frequency
Survey (patient participants and SPs)	Baseline, 6mo, 9mo, 15mo
A1c test (patient participants)	Baseline, 6mo, 9mo, 12mo, 15mo
Diabetes educational materials (patient participants and SPs)	Baseline and quarterly (4x per year)
FAMS 2.0 mobile phone intervention (patient participants)	Approx. 2 texts per day for 9 months
FAMS 2.0 mobile phone intervention (SPs)	Approx. 4-5 texts per week for 9 months
FAMS 2.0 phone coaching (patient participants)	Approx. 25-30 min. calls once a month for nine months

All data were stored in REDCap. Information collected as part of regular care was collected from patient participants' EMR (e.g., birthdate, gender, A1c test results, height, weight, BMI, medications, co-morbidities, etc.). Surveys were administered to all participants at baseline, 6, 9, and 15 months—online, mailed copy, or by telephone. A1c results were collected from persons with diabetes with each survey as well as at 12 months. Participants received mail-in HbA1c test kits provided by CoreMedica Laboratories. HbA1c values collected as part of clinical care were also extracted from the EMR.

Patient participants assigned to control group:

Text messages - Patient participants received a text message when their A1c result was ready (baseline, 6mo, 9mo, 12mo, 15mo).

Patient/SP dyads assigned to FAMS intervention:

Phone coaching - Patient participants completed a phone coaching session with a trained coach once a month for nine months (10 total sessions; 9 core sessions and a brief 10th wrap-up session). Coaching sessions lasted 25-30 minutes each. Coaching sessions included:

- Setting a behavioral goal that can be completed at least 4 days per week in the categories of dietary behavior, physical activity, or stress management (setting and/or adjusting the goal, check in on goal progress)
- Skill building around family/friend involvement in diabetes management, specific to the goal (discussion of helpful and/or harmful family involvement, coach-selected skill building to align with and address the patient participant's experiences, setting a verbal contract to practice the learnt skill with a specific identified person and – at subsequent sessions – check in on how that went).

FAMS 2.0 (PI: [name])

R01-DK119292

NCT04347291

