Text messages - Patient participants received a text message when their A1c result was ready (Baseline, 6mo, 9mo, 12mo, 15mo). They also received approximately 2 texts per day for 9 months:

- 3 to 4 one-way texts per week pertaining to goal set in the patient participant's most recent coaching session; sent randomly within a window of time identified as convenient by the patient participant
- 3 to 4 one-way texts per week pertaining to medication adherence barriers identified as relevant by the patient participant during the baseline survey; sent randomly within a window of time identified as convenient by the patient participant
- 1 daily interactive medication assessment messages sent shortly before the patient participants' bedtime (e.g., "Did you take all of your diabetes medications as directed today, Tues, Jan 18, 2022? Please reply Yes or No.")
- 1 weekly interactive text asking about goal progress to be followed by feedback text from coach within the next few days (e.g., "This week is done! Your SMART goal was to walk 20 mins each day for 6 days. What went well or got in your way? Reply with the number of days you met your goal and a brief reflection.")

Support persons received approximately 4-5 texts per week for 9 months:

- 3 to 4 one-way texts per week pertaining to supporting the patients' self-care efforts and increasing dialogue about diabetes and health behaviors with the patient participant; tailored to the goal "type" set in the patient participant's most recent coaching session; sent randomly within a window of time identified as convenient by the support person participant.
- 1 interactive text per week about supporting the patient participant in their diabetes self-care; sent at a time of day identified as convenient by the support person participant. Responses received an automated message. (e.g., "This week is done! Reflect on how you supported [patient participant name] this week. Reply with what went well or what could go better next week"; "How confident do you feel supporting [patient participant name] with her health goals? Please provide a rating from 1 to 5 where 1=not so confident and 5=very confident")

Summary of Measures:

Construct	Instrument or Source
Patient Participants	
Outcomes	
Hemoglobin A1c (primary outcome)	Venipuncture or point-of-care device used in regular clinical care collected from the electronic medical record or collected via mail-in kit from CoreMedica

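### In the 9-month mediation models the 9-month mediators are measured with the outcome, so an effect of the outcome on the mediator can be reported as mediation

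*SAP*

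**What the plan says.** The mediation paragraph of the SAP says "we model between-subjects mediation with path analysis with an SEM framework". On timing it says "Mediation models include intervention targets at both 6 and 9 months as mediators and a single outcome", and then "We ran this model separately for each outcome at 9, 12 (H1cA1c only) and 15 months". One mediator set therefore serves every outcome time, including 9 months.

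Protocol section 5.0 gives the schedule. "Surveys were administered to all participants at baseline, 6, 9, and 15 months", and "A1c results were collected from persons with diabetes with each survey as well as at 12 months". Section 5.0 also lists the mediators (self-efficacy, self-care, family and friend involvement) as questionnaire scales, along with distress and well-being.

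On interpretation, the SAP says that "indirect effects will identify mechanisms by which FAMS 2.0 affected outcomes".

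Neither document removes the 9-month mediators from the 9-month models, adjusts for the 6-month outcome, plans a reverse or cross-lagged path or a sensitivity analysis, or limits the 9-month results to association.

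**The concern.** A mediation model assumes that the mediator acts on the outcome. When both are measured at one visit, the data cannot separate that from the outcome acting on the mediator. The reverse direction is plausible here: a patient who is less distressed may well report more self-efficacy or less criticism from family. If the intervention lowers distress by another route, the 9-month mediators would follow, and the model would credit them with the effect.

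Mediation is part of Aim 4 (protocol section 2.0), and the SAP names SEM as one of its two primary model types. At stake is which component is said to have worked by the end of the intervention, and so what a later version of FAMS would keep. The primary A1c comparison between arms is not affected.

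**Working it through.** **Timing, set side by side**

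| Outcome time | 6-month mediators | 9-month mediators |
|---|---|---|
| 9 months (A1c, distress, well-being) | earlier | same assessment |
| 12 months (A1c only) | earlier | earlier |
| 15 months (A1c, distress, well-being) | earlier | earlier |

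**The plan's own figures (protocol section 8.0).** Difference 0.5, SD 1.5, 80% power and two-sided 5% give 142 per arm, 284 in total. Dropout of 15% gives 284/0.85 = 334.1, against the stated 334. These figures reproduce. They supply the n and a standardized effect of 0.5/1.5 = 0.333. No figure is given for mediation.

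**Why a false indirect effect arises.** Let the mediator have no effect on the outcome, and let the outcome move the mediator by r at the same visit. Take outcome autocorrelation 0.6, mediator autoregression 0.5, mediator residual variance 0.75 and a treatment effect d on the outcome at both 6 and 9 months. The baseline mediator and baseline outcome are adjusted (the SAP does not state the covariates of the mediation models). Then:

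- Treatment to 9-month mediator: a = r·d + 0.5·r·d = 1.5·r·d.
- 9-month mediator to 9-month outcome: b = r·v / (r²·v + 0.75), where v is the residual variance of the 9-month outcome given arm, baseline values and the 6-month mediator.

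For r = 0.3 and d = 0.333:

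- a = 1.5 × 0.3 × 0.333 = 0.150.
- The 6-month outcome has variance 0.64 given arm and baseline. Given the 6-month mediator too, this is 0.64 × 0.75 / (0.09 × 0.64 + 0.75) = 0.594.
- v = 0.36 × 0.594 + 0.64 = 0.854.
- b = 0.3 × 0.854 / (0.09 × 0.854 + 0.75) = 0.310.
- a × b = 0.150 × 0.310 = 0.046 SD, although true mediation is zero.

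Simulation of this model gave a mean of 0.047 SD, or 0.047/0.333 = 14% of the total effect. For r = 0.2 and 0.5 the means were 0.025 and 0.102 SD (8% and 31%).

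**How often it would be declared significant** (n = 284, true mediation zero, 95% interval for the indirect effect excludes zero):

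| Model for the 9-month outcome | Run 1 | Run 2 (r = 0.2 / 0.3 / 0.5) |
|---|---|---|
| 6- and 9-month mediators, path through 9 months (planned) | 13-51% | 25% / 30% / 46% |
| 6-month mediator only | 3-21% | 4% / 14% / 34% |
| 6-month mediator, 6-month outcome adjusted | 0.3-0.6% | 1% / 2% / 2% |

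Run 1 used reverse effects of -0.2 to -0.4, treatment effects of -0.3 to -0.4 SD, autocorrelations of 0.6 and 0.4, and 1,500 trials per scenario. Run 2 used d = 0.333, mediator autoregression 0.5, bias-corrected bootstrap intervals (1,000 resamples) and 300 trials per scenario, with Monte Carlo error up to about 3 points. With r = 0, run 2 gave about 1% for the planned model. Further runs at the run 1 values gave about 12-50% for the planned 9-month model.

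**Later outcomes.** The 9-month outcome can drive both the 9-month mediator and the 12-month outcome, so it confounds that path even though the order in time is right. At the run 1 values, false positives at 12 months were about 5-46%. The 15-month model has the same structure but was not simulated.

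**Cost of adjusting for the earlier outcome.** When true mediation was simulated, detection fell from 69-94% to 21-51% in one set of scenarios, and from over 95% to about 50% in another.

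**The case against.** The strongest reply is that the size is assumed. The reverse effects and autocorrelations appear in neither document, each simulation has a single mediator where the SAP plans several, and with no reverse effect the planned model gave about 1%. All of this stands. It limits the number attached to the problem, but it does not give time order to measurements taken together. Figure 1 is not available here and may show sequential paths; these would not create order within a visit either.

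A second reply is that the analysis is not primary, and that 12- and 15-month models are already planned. The first part is true and limits the severity. The second helps less than it seems, because those models also lack a stated adjustment for the 9-month outcome.

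A reader might infer more than the documents support:

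- **That the A1c texts create the same-visit problem.** Section 5.0 says "Patient participants received a text message when their A1c result was ready". The kit is mailed in, so the 9-month result is unlikely to be known when the 9-month survey is answered. An earlier result acting on later mediators is a lagged path. For A1c the concurrent argument rests on glycemic state itself affecting answers, and is weaker than for distress and well-being.
- **That the dyadic models share the defect.** The SAP describes change in one variable explaining change in another and gives no time points, so no same-visit problem is shown.
- **That dropping the 9-month mediators is enough.** The 6-month-only rows above show that it is not.

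**Conclusion.** The concern holds for the paths from 9-month mediators to 9-month outcomes. The planned model cannot tell mediation from an effect of the outcome on the mediator, and the SAP's wording about mechanisms claims more than it can show. Under the stated assumptions, with zero true mediation, about 12-50% of trials would give a false significant 9-month indirect effect. The case is clearest for distress and well-being, which share a survey with the mediators.

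It would go too far to say that reverse causation will be reported as mediation: in most of the assumed scenarios fewer than half of trials were falsely positive, and without a reverse effect almost none were. It would equally be wrong to treat the 12- and 15-month models as safe because they are ordered in time.

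**What to change.** In the SAP:

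1. Describe indirect effects through 9-month mediators on 9-month outcomes as associations, not mechanisms.
2. Add a lagged analysis for the 9-month outcomes: 6-month mediators only, adjusted for the baseline mediator, the baseline outcome and the 6-month outcome.
3. For the 12- and 15-month outcomes, add a version of the planned model adjusted for the 9-month outcome.
4. Report these beside the planned models, and base mechanism claims on agreement between the two.
5. State the time points of the dyadic models, so that their ordering can be judged.

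No new data are needed: A1c, distress and well-being are all collected at 6 and 9 months. The cost is some re-analysis, since the SAP describes these models as already run, and lower power. The adjusted models also remove true mediation already expressed in the earlier outcome, so a null result from them alone does not rule mediation out.

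### Mediators are restricted using their estimated intervention effects in the same data that then give the indirect effects, so results for retained mediators can be biased away from zero and 95% coverage is not assured

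*SAP*

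**What the plan says.** The SAP works in sequence. It first estimates the arm difference on every target: "For each intervention target (Figure 1), we fit models as described above", at 6, 9 and 15 months. It then turns to mediation: "Mediation models include intervention targets at both 6 and 9 months as mediators and a single outcome". For parsimony, "we restricted the number of mediators guided by findings evaluating intervention effects on these mediators", and for self-care the choice is described as "opting for continuous and sensitive mediator measure(s) of self-care behaviors unless both measures were significantly improved by the intervention".

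Inference on the retained mediators follows: "Path coefficients and indirect effects evaluate mediation using 2,000 bootstrap samples for bias-corrected estimates and 95% confidence intervals for effects". Two conclusions are to be drawn. On the first half of each indirect effect, "Paths from condition to mediators will determine if FAMS 2.0 improved each mediator relative to control". On the product, "indirect effects will identify mechanisms by which FAMS 2.0 affected outcomes".

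The SAP gives no threshold or time point for the general restriction. It describes no split sample, no selection step inside the bootstrap and no sensitivity model with all hypothesized mediators. Patient-level mediation is not labelled exploratory: Protocol section 2.0, Aim 4, speaks of testing hypothesized mediators, and the SAP counts structural equation modeling among its two primary models. The exploratory label in the SAP attaches to mediation of support person outcomes through patient outcomes.

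**The concern.** An indirect effect is the product of the condition-to-mediator path (a) and the mediator-outcome path (b). If a mediator enters the model partly because its estimated a was large, that estimate is no longer unbiased given entry: measures with lucky errors are over-represented among those kept. Re-estimating a in the same participants reproduces the luck. Bootstrap samples drawn after selection treat the retained list as if it had been fixed beforehand, so the intervals carry no allowance for the choice.

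At stake is what Aim 4 can say about mechanism. A weak mediator that is retained may look much stronger than it is, and a null one that is retained by chance may be reported as a mechanism. Because the rule is not stated, a reader can neither reproduce the selection nor correct for it.

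**Working it through.** **Inputs.** From Protocol section 8.0: difference 0.5%, SD 1.5%, 5% level (two-sided assumed), 80% power, effective n=284 (142 per arm), dropout about 15%, target 334, detectable standardized effect on mediators 0.32–0.34. From the Protocol's Summary of Measures: ten patient target measures. Assumed, because the documents give no value: b=0.3 (range below), normal errors with unit residual SD, one mediator at one wave, and a strict p<0.05 screen on the arm comparison.

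**The plan's own figures.**
- n per arm = 2(1.960+0.842)²×1.5²/0.5² = 141.3, so 142, total 284; 334×0.85 = 283.9.
- Detectable effect = 2.802×√(2/n per arm). At 80% retention (133.6 per arm) it is 0.343; at 90% (150.3 per arm) it is 0.323.

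These reproduce. The documents state no figure for bias or coverage of indirect effects.

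**Analytic check of the inflation.** Let SE = √(2/142) = 0.1187, t = d/SE and c = 1.96. Given significance in the beneficial direction, the expected standardized estimate is t + φ(c−t)/[1−Φ(c−t)].
- d=0.1: t=0.843; 0.843 + 0.2138/0.132 = 2.463; ratio 2.92.
- d=0.2: t=1.685; 1.685 + 0.3841/0.392 = 2.665; ratio 1.58.
- d=0.33: t=2.781; 2.781 + 0.2849/0.794 = 3.140; ratio 1.13.
- d=0: 0.0584/0.025 = 2.34 SE, or 0.277 SD; times b=0.3 gives 0.083 against a true 0.

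**Simulation of the indirect effect.** n=284, 1:1, b=0.3, done in two ways: a two-sided screen with a 2,000-sample bias-corrected bootstrap (4,000 trials per setting), and a beneficial-direction screen with a Monte Carlo interval for the product. Ranges span the two where both apply.

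| True effect on mediator | Kept (two-sided screen) | Mean retained ÷ true | Coverage if retained |
|---|---|---|---|
| 0 SD | 4.8% | 0.083 against 0 (beneficial direction) | 0–7% |
| 0.1 SD | 14.0% | 0.081/0.030=2.7 to 0.087/0.030=2.9 | 80–86% |
| 0.2 SD | 39.6% | 0.095/0.060 to 0.096/0.060=1.6 | 94–96% |
| 0.3 SD | not run | 0.107/0.090=1.19 | 98% |
| 0.33 SD | 78.7% | 1.12–1.15 | about 97% |
| 0.5 SD | 98.9% | 1.01 | 97% |

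Without the screen, the bootstrap run was essentially unbiased, with coverage of 93–96% across these effects.

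**Dependence on b.** For a null mediator that is retained, the share of 95% intervals excluding zero is about 93–100% at b=0.3, about 80% at 0.2, about 27% at 0.1 and about 3% at 0.

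**False positives.** With a=0 and b=0.3, a mediator is both kept and declared in 4.8% of trials. With no screen it is declared in 6.9%.

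**The case against.** The strongest reply is that the SAP does not describe a significance screen. A reader might infer one, but the general wording is only that findings guided the choice. Significance appears once, for keeping a second measure of a self-care behavior, and the default is a continuous, sensitive measure. The Protocol lists two measures each for diet and medication adherence, so the explicit clause has narrow reach. This stands: the text shows a data-driven rule that is not specified, and the strict screen above is an illustration.

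A reader might also infer that every reported indirect effect is inflated and every interval fails. That does not follow. At 0.33 SD the bias is about 12–15% with coverage near 97%. The damage is concentrated in weak or null mediators.

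Nor does the screen create extra false mediators. A non-zero indirect effect already needs a non-zero condition-to-mediator path, and the rate for a null mediator fell from 6.9% to 4.8%. That several null measures give some chance of at least one significant arm difference (1−0.95¹⁰ = 40% for ten independent ones) is ordinary multiplicity and would exist without selection.

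Finally, the simulation has one mediator at one wave. The SAP's models have several at two waves, so the relevant b is a partial path and could be smaller than 0.3. The SAP's target models also adjust for baseline, which would raise power and reduce inflation at a given true effect. Parsimony is a fair aim too: ten measures at two waves would be 20 mediators in about 284 people.

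What remains untouched is that the choice uses one component of the indirect effect, in the same participants, and the described inference ignores it.

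**Conclusion.** The point holds as a defect of specification and of inference after selection. Mediators are restricted with reference to their own estimated arm effects, by a rule the SAP does not state, and the same paths are then tested with intervals that take no account of that choice. Indirect effects for retained mediators can be biased away from zero, and nominal coverage is not assured.

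The size runs from serious when the true effect on the mediator is null or about 0.1 SD, through a 1.6-fold overstatement with near-nominal coverage at 0.2 SD, to minor at the effect the trial could detect. These figures rest on the assumed strict screen, b=0.3 and a single mediator; a looser rule or better-powered models would give less. Only the mediation part of Aim 4 is affected. The HbA1c comparison and the secondary outcome comparisons are not. This should be changed, but it does not threaten the trial's main result.

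**What to change.** In the SAP's mediation paragraph, fix the mediator list from the conceptual framework without reference to arm differences. Name one measure per construct, chosen on measurement grounds; this extends the SAP's existing preference for continuous, sensitive measures. Delete the clause that keeps a second measure "unless both measures were significantly improved by the intervention". Report every mediator on the list, whatever its result.

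The framework gives six patient constructs: self-efficacy (1), self-care behaviors (3) and helpful and harmful involvement (2). At two waves that is 6×2 = 12 mediator variables, against 10×2 = 20 if all measures entered, so most of the parsimony is preserved.

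If a data-driven restriction is kept, state the rule, including threshold and time point, repeat it inside each bootstrap sample, and label the selected-mediator results exploratory.

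The cost is SAP wording and re-running the path models; no new data are needed. The downside is a path model somewhat larger than the restricted one, with possibly wider intervals. That widening was not computed, and using one measure per construct should keep it small.
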